---

## PROTOCOL AMENDMENT SUMMARY OF CHANGES TABLE

Amendment 3.0 (Version 4.0): (XX month 2023)

This amendment is considered to be substantial based on the criteria set forth in Article 10(a) of Directive 2001/20/EC of the European Parliament and the Council of the European Union.

### Overall Rationale for the Amendment

The main purpose of the amendment is the removal of the fasting restriction after end of Cycle 24, change to 1st key secondary endpoint estimand and include an additional key secondary endpoint.

### Summary of Changes

Section Number and Name	Description of Change	Brief Rationale
Section 1.1, Section 3, Section 9.4.2.1	Include intercurrent event strategy for primary estimand	In line with ICH E9 (R1) addendum
Section 1.1, Section 3, Section 9.4.2.2.1	Update 1 st key secondary estimand	To address regulatory feedback
Section 1.1, Section 3, Section 9.4.2.2.2	Upgrade secondary estimand PlexiQOL to an additional key secondary estimand of PlexiQOL	Update to company position that PlexiQOL intended for labelling purposes
Section 9.1, Section 9.5	Modify MTP to include 2 nd key secondary estimand PlexiQOL and further information (scenarios) about the testing of key secondary endpoints	Update to company position that PlexiQOL intended for labelling purposes and to clarify the testing strategy within a key secondary endpoint.
Section 1.1, Section 3, Sections 9.4.2.3.7, 9.4.2.3.9, 9.4.2.3.10, 9.4.2.3.11, 9.4.2.3.13	Add estimate at each scheduled visits other than overall estimate over randomised treatment period for the following secondary endpoints: chronic target PN pain palliation, pain medication use, PII-pNF pain interference total score, PROMIS Physical Function scores, PedsQL (NF1 module acute version 3.0 – adult report ) skin sensations domain, EQ-5D-5L and EQ-VAS	To align with change to key secondary estimand to address regulatory feedback
Section 8.1.8	Remove endpoints description	Not applicable to this section
Appendix A7	Updated information about retention timelines of records and documents to 25 years after study archiving or as required by local regulations	Update required to comply with EU CTR and global company requirement

Section Number and Name	Description of Change	Brief Rationale
Section 1.1, 1.3; Table 1: Schedule of Activities; Section 5.2.1 and 6.1.1	Added the following wording to lift the fasting restriction from the end of C24: From the end of Cycle 24 (Cycle 25 Day 1) participants will not be required to continue to observe the fasting restriction, i.e participant can eat at any time point in relation to each medication intake (study intervention capsules). Refer to Section 5.2.1 for the definition of participant fed state.	To allow study drug to be administered in the fed state; modification follows an updated and more complete analysis of the food effect data for the program
Section 1.1 and Section 4.1	Added detail about the food restriction lifting after C24	To align with removal of fasting restriction after C24; modification follows an updated and more complete analysis of the food effect data for the program
Section 1.1 and Section 3 and section 9.3 (Table 12)	Added an exploratory objective re efficacy in fed state after C24 and related new analysis set	To align with removal of fasting restriction after C24; modification follows an updated and more complete analysis of the food effect data for the program
Section 8.1.1 and 8.1.8	Added text to clarify that if a participant taking part in the study had a target PN resection and remained in the study, MRI scans and PAINS-pNF data will continue to be collected.	Clarification
Global	Minor editorial changes to wording and formatting	To aid readability

bid, Twice daily; BSA, Body surface area; C1D1, Cycle 1 Day 1; CFR, Code of Federal Regulations; CTIS, Clinical Trials Information System; CYP, Cytochrome P450; EU, European Union; FDA, Food and Drug Administration; ICH, International Conference on Harmonisation; IEC, Independent Ethics Committee; IOP, Intraocular pressure; IRB, Institutional Review Board; IRT, Interactive Response Technology; NF1, Neurofibromatosis type 1; PN, Plexiform neurofibroma; PK, Pharmacokinetics; UK, United Kingdom.

## 1 PROTOCOL SUMMARY

### 1.1 Synopsis

#### Protocol Title:

A Phase III, Multicentre, International Study with a Parallel, Randomised, Double-blind, Placebo-controlled, 2 Arm Design to Assess the Efficacy and Safety of Selumetinib in Adult Participants with NF1 who have Symptomatic, Inoperable Plexiform Neurofibromas (KOMET).

#### Short Title:

Efficacy and Safety of Selumetinib in Adults with NF1 who have Symptomatic, Inoperable Plexiform Neurofibromas (KOMET).

#### Rationale:

Selumetinib has been shown to be effective in the treatment of paediatric patients with NF1 who have symptomatic, inoperable PN and is approved in the US for the treatment of paediatric patients aged  $\geq$  2 years of age. Plexiform neurofibromas, whilst typically present at birth, can continue to manifest through late adolescence and early adulthood (Williams et al 2009) and are often associated with significant clinical symptoms including pain and motor dysfunction (Gross et al 2018). As spontaneous PN shrinkage and spontaneous resolution of symptoms associated with PN has been shown to be extremely unlikely (Akshintala et al 2020, Gross et al 2018), adults with NF1-PN continue to have a significant unmet need. This study will aim to inform the benefit risk profile of selumetinib in adults with NF1 who have symptomatic, inoperable PN.

#### Objectives and Endpoints

Objectives	Estimands descriptions/Endpoints
Primary  To compare the effect of selumetinib relative to placebo by assessment of confirmed partial and complete response rate (ORR) by end of Cycle 16 using volumetric MRI analysis as determined by ICR (per REiNS criteria) in participants with NF1 who have symptomatic, inoperable PN.	Objective response rate is defined as the proportion of participants who have a confirmed CR (defined as disappearance of the target PN, confirmed by a consecutive scan within 3 to 6 months after the first response) or confirmed PR (defined as a target PN volume decrease $\geq$ 20%, compared to baseline, confirmed by a consecutive scan within 3 to 6 months after the first response) by end of Cycle 16 as determined by ICR per REiNS criteria.  The analysis will include all randomised participants with measurable target PN at

Objectives	Estimands descriptions/Endpoints
	baseline per ICR. Data obtained while on-treatment from first dose up until progression (if progression occurs prior to end of Cycle 16), or the last evaluable assessment up to and including end of Cycle 16 in the absence of progression, will be included in the assessment of ORR. The measure of interest is the difference in ORR. See statistical considerations section 9.4.2.1 for the complete intercurrent events strategy.
Key Secondary	
To compare the effect of selumetinib relative to placebo by assessment of change in chronic target PN pain intensity from baseline in participants with a PAINS-pNF chronic target PN pain score of $\geq 3$ at baseline.	Difference of the means in the change from baseline in PAINS-pNF chronic target PN pain intensity score at Cycle 12 between selumetinib and placebo amongst participants with a PAINS-pNF chronic target PN pain intensity score $\geq 3$ at baseline, and at least one post-baseline average cycle PAINS-pNF chronic target PN pain intensity score, regardless of changes to the participants' chronic PN pain medication (treatment policy strategy). See statistical considerations sections 9.4.2.2 for the complete intercurrent events strategy.
To compare the effect of selumetinib relative to placebo by assessment of change in HRQoL from baseline in participants with NF1 who have symptomatic, inoperable PN.	Difference in the change from baseline in PlexiQoL total score at Cycle 12 between selumetinib and placebo amongst participants with a PlexiQoL total score at baseline and at least one post-baseline total score. See statistical considerations section 9.4.2.2.2 for the complete intercurrent events strategy.
Secondary	
To demonstrate the effectiveness of selumetinib by assessment of confirmed partial and complete response rate (ORR) using volumetric MRI analysis as determined by ICR (per REiNS criteria) in participants with NF1 who have symptomatic, inoperable PN.	This ORR analysis will include all participants randomised to selumetinib with measurable target PN at baseline per ICR and who received at least one dose of selumetinib, ie, single arm assessment of ORR. Data obtained while on-treatment from first selumetinib dose up until progression, or the last evaluable assessment in the absence of progression, will be included in the assessment of ORR.

Objectives	Estimands descriptions/Endpoints
To demonstrate the effectiveness of selumetinib by assessment of DoR in participants with NF1 who have symptomatic, inoperable PN.	The duration of response will be defined as the time from the date of first documented response (which is subsequently confirmed) until date of documented progression by ICR per REiNS criteria or death due to any cause. The analysis will include all participants randomised to selumetinib with measurable target PN at baseline per ICR who received at least one dose of selumetinib and with a confirmed CR or confirmed PR prior to study intervention discontinuation. Duration of response will be derived using while on-treatment MRI volumetric assessments.
To demonstrate the effectiveness of selumetinib by assessment of PFS in participants with NF1 who have symptomatic, inoperable PN.	Progression free survival is defined as the time from the date of first selumetinib dose until date of progression by ICR per REiNS criteria or death (due to any cause). The analysis will include all participants randomised to selumetinib with measurable target PN at baseline per ICR who received at least one dose of selumetinib. Progression free survival will be derived using while on-treatment MRI volumetric assessments.
To demonstrate the effectiveness of selumetinib by assessment of TTP in participants with NF1 who have symptomatic, inoperable PN.	Time to progression is defined as the time from the date of first selumetinib dose until date of documented objective disease progression by ICR per REiNS criteria. The analysis will include all participants randomised to selumetinib with measurable target PN at baseline per ICR who received at least one dose of selumetinib. Time to progression will be derived using while on-treatment MRI volumetric assessments.

Objectives	Estimands descriptions/Endpoints
To demonstrate the effectiveness of selumetinib by assessment of TTR in participants with NF1 who have symptomatic, inoperable PN.	Time to response is defined as the time from date of first selumetinib dose until the date of first documented objective response (which is subsequently confirmed), by ICR per REiNS criteria. The analysis will include all participants randomised to selumetinib with measurable target PN at baseline per ICR and who received at least one dose of selumetinib and with a confirmed CR or confirmed PR prior to selumetinib discontinuation. Data obtained from first dose up until progression, or the last evaluable assessment in the absence of progression, will be included in the assessment of TTR. Time to response will be derived using while on-treatment MRI volumetric assessments.
To demonstrate the effect of selumetinib relative to placebo by assessment of percentage change from baseline in target PN volume in participants with NF1 who have symptomatic, inoperable PN.	Difference in best percentage change from baseline in target PN volume by ICR per REiNS criteria between selumetinib and placebo during the randomised period. The analysis will include all participants randomised to study intervention with measurable target PN at baseline per ICR. The best percentage change from baseline in target PN volume will be derived using while on-treatment MRI volumetric assessments during the randomised period.
To compare the effect of selumetinib relative to placebo by assessment of chronic target PN pain palliation and time to chronic target PN pain palliation in participants with a PAINS-pNF chronic target PN pain score of $\geq 3$ at baseline.	
Chronic target PN pain palliation is defined as improvement of <math>\geq 2</math> in average cycle PAINS-pNF chronic target PN pain intensity score and no increase in chronic PN pain medication compared to baseline for that cycle. Pain palliation will be assessed in participants with a PAINS-pNF chronic target PN pain score of <math>\geq 3</math> at baseline.
 
 
• Difference in proportion of participants with chronic target PN pain palliation between selumetinib and placebo at post-baseline cycles and overall over the randomised treatment period.
 
• Time to chronic target PN pain palliation is defined as the time from the first dose of study drug until the cycle of chronic target PN pain palliation.
 

Objectives	Estimands descriptions/Endpoints
To compare the effect of selumetinib relative to placebo by assessment of pain medication compared with baseline.	Difference in change from baseline in pain medication use (as reported using the eDiary) and as assessed by the investigator) between selumetinib and placebo at post-baseline cycles and overall over the randomised treatment period.
To compare the effect of selumetinib relative to placebo by assessment of pain interference compared with baseline.	Difference in change from baseline in PII-pNF pain interference total score between selumetinib and placebo at post-baseline cycles and overall over the randomised treatment period.
To compare the effect of selumetinib relative to placebo by assessment of physical functioning compared with baseline.	Difference in change from baseline in PROMIS Physical Function scores between selumetinib and placebo at post-baseline cycles and overall over the randomised treatment period.
To compare the effect of selumetinib relative to placebo by further assessment of HRQoL compared with baseline.	Difference in change from baseline in the Skin Sensations domain from the PedsQL (NF1 module acute Version 3.0 – adult report) between selumetinib and placebo at post-baseline cycles and overall over the randomised treatment period.
To compare the effect of selumetinib relative to placebo by assessment of health status compared with baseline.	Difference in change from baseline in EQ-5D-5L between selumetinib and placebo at post-baseline cycles and overall over the randomised treatment period.
	Difference in change from baseline in EQ-VAS between selumetinib and placebo at post-baseline cycles and overall over the randomised treatment period.
To evaluate the effect of selumetinib by assessment of physical functioning compared with baseline.	Change from baseline in PROMIS Physical Function items.
To evaluate the effect of selumetinib by assessment of HRQoL compared with baseline.	Change from baseline in PlexiQoL.
	Change from baseline in the Skin Sensations domain from the PedsQL (NF1 module acute Version 3.0 – adult report).

Objectives	Estimands descriptions/Endpoints
To evaluate the effect of selumetinib by assessment of health status compared with baseline.	Change from baseline in EQ-5D-5L (standardised measure of health status). Five dimensions (mobility, self-care, usual activities, pain/discomfort, anxiety/depression). Change from baseline in EQ-VAS.
To assess the PK of selumetinib.	

• Plasma concentrations and PK parameters of selumetinib including, but not limited to:

◦ Cmax, AUC(0-6), AUC(0-8), AUClast, CL/F, Vss/F, tmax, tlast derived after multiple dose administration.

• Plasma concentrations and PK parameters of N desmethyl selumetinib including, but not limited to:

◦ Cmax, AUC(0-6), AUC(0-8), AUClast, tmax, tlast derived after multiple dose administration.

◦ MPAUC and MPCmax after multiple dose administration.

 
Population PK-pharmacodynamic analyses will be completed to investigate the selumetinib exposure-response relationship for safety and efficacy. The analyses will be reported separately from the Clinical Study Report.


Safety
 
To assess the safety and tolerability of selumetinib alone and as compared to placebo in adult participants with NF1 who have symptomatic, inoperable PN.
	
Safety and tolerability will be evaluated in terms of AEs, vital signs, clinical laboratory assessments, urinalysis, physical exam, ECG (as clinically indicated), ECHO/cardiac MRI and ophthalmologic assessment. The safety analysis will include all randomised participants who receive at least one dose of study intervention.
 
Assessments related to AEs cover:
 
 
• Occurrence/Frequency
 
• Relationship to IP as assessed by investigator
 
• CTC grade
 
• Seriousness
 
• Death
 
• AEs leading to discontinuation of IP
 
• Other action taken related to IP
 
• AEs of special interest
 
• Other significant AEs
 
 
Vital signs parameters include systolic and diastolic BP, and pulse rate, respiration rate, oxygen saturation, body temperature and body weight.
 
Assessments cover:
 
 
• Observed value
 
• Absolute change from baseline values over time
 
 
Laboratory parameters include clinical chemistry and haematology parameters as well as urinalysis.
 
Assessments cover:
 
 
• Observed value
 
• Absolute change from baseline values over time
 
 
Echocardiogram/cardiac MRI assessments include measurement of LVEF.
 
Assessments cover:
 
 
• Observed value
 
• Absolute change from baseline values over time
 
 
Ophthalmologic assessments include best corrected visual acuity, IOP, and slit-lamp fundoscopy.
 
Assessments cover:
 
 
• Observed value
 

Exploratory
 
To evaluate PFS during the randomised period on selumetinib and placebo in participants with NF1 who have symptomatic, inoperable PN.
	
Progression free survival is defined as the time from the date of first dose until date of progression by ICR per REiNS criteria or death (due to any cause). The analysis will include all randomised participants. Progression free survival will be derived using while on-treatment MRI volumetric assessments.

To compare the effect of selumetinib relative to placebo by assessment of spike target PN pain intensity.	Difference in change from baseline in PAINS-pNF spike target PN pain intensity between selumetinib and placebo at post-baseline cycles and overall over the randomised treatment period.
To explore potential biomarkers in residual biological samples, which may influence the progression of neurofibromatosis and inoperable plexiform neurofibromas (and associated clinical characteristics) and/or identify participants likely to respond to selumetinib or, may be surrogate markers of response.	Exploratory biomarker analysis that may include (but is not limited to) change from baseline in the expression and activity of neurofibromatosis and MEK pathways and/or specific RNA transcripts (arrays) as a surrogate for protein expression
The following exploratory objectives will be assessed over the entire duration of the study in all participants	
To evaluate effect of selumetinib by assessment of chronic target PN pain intensity compared to baseline.	Change from baseline in PAINS-pNF chronic target PN pain intensity score.
To evaluate effect of selumetinib by assessment of spike target PN pain intensity compared to baseline.	Change from baseline in PAINS-pNF spike target PN pain intensity score.
To evaluate effect of selumetinib by assessment of chronic target PN pain palliation in participants with a PAINS-pNF chronic target PN pain score of $\geq 3$ at baseline.	Chronic target PN pain palliation is defined as improvement of $\geq 2$ in average cycle PAINS-pNF chronic target PN pain intensity score and no increase in chronic PN pain medication compared to baseline for that cycle. Pain palliation will be assessed in post baseline cycles in participants with a PAINS-pNF chronic target PN pain score of $\geq 3$ at baseline.
To evaluate effect of selumetinib by assessment of pain interference compared to baseline.	Change from baseline in PII-pNF pain interference total score.
To evaluate effect of selumetinib by assessment of pain medication compared to baseline.	Change from baseline in pain medication: 
 
As reported using the e-Diary.
 

To evaluate the efficacy of selumetinib based on NF1 mutation alteration patterns	Differences in ORR, PN pain intensity in subgroups if feasible based on NF1 mutation alteration patterns
Exploratory endpoints assessed after end of Cycle 24 in fed conditions	
To evaluate efficacy under fed dosing of selumetinib	Percentage change from baseline in target PN volume at Cycle 30 and 36.

AE, adverse event; AUC(0-6), area under the concentration-time curve from time 0 to 6 hours; AUC(0-8), area under the concentration-time curve from time 0 to 8 hours; AUClast, area under the concentration-time curve from time 0 to time of last quantifiable concentration; BP, blood pressure; CL/F, apparent total body clearance of the drug from plasma after extravascular administration; Cmax, maximum observed concentration; CR, complete response; CTC, Common Terminology Criteria; DoR, duration of response; ECG, electrocardiogram; ECHO, echocardiogram; EQ-5D-5L, EuroQol 5-Dimension 5-level; EQ-VAS, EuroQol visual analogue scale; HRQoL, health related quality of life; ICR, independent central review; IOP, intraocular pressure; IP, investigational product; LVEF, Left ventricular ejection fraction; MEK, Mitogen activated protein kinase; MPAUC, Metabolite:parent ratio based on AUC; MPCmax, Metabolite:parent ratio based on Cmax; MRI, magnetic resonance imaging; NF1, Neurofibromatosis type 1; ORR, Objective response rate; PAINS-pNF, PAin INTensity Scale for Plexiform Neurofibromas; PedsQL, Paediatric Quality of Life Inventory; PFS, Progression free survival; PII-pNF, Pain interference index – plexiform neurofibroma; PK, pharmacokinetic(s); PlexiQoL, Plexiform Neurofibroma Quality of Life scale; PN, Plexiform neurofibroma(s); PR, partial response; PROMIS, Patient-Reported Outcomes Measurement Information System; REiNS, Response Evaluation in Neurofibromatosis and Schwannomatosis; tlast, time of last observed concentration; RNA, Ribonucleic acid; tmax, time to reach maximum observed concentration following drug administration; TTP, time to progression; TTR, time to response; Vss/F, volume of distribution (apparent) at steady state after extravenuous administration.

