### **8.3.5 Adverse Events Based on Examinations and Tests**

The results from the CSP-mandated laboratory tests, vital signs, physical examinations, ECGs, and ECHO/cardiac MRI scans will be summarised in the Clinical Study Report.

Deterioration as compared with baseline in protocol-mandated laboratory values, vital signs, physical examinations, ophthalmologic examinations, ECGs and ECHO/cardiac MRI should therefore only be reported as AEs if they fulfil any of the SAE criteria, are the reason for discontinuation of treatment with the study intervention or are considered to be clinically relevant as judged by the investigator (which may include but not limited to consideration as to whether treatment or non-planned visits were required or other action was taken with the study intervention, eg, dose adjustment or study intervention interruption).

If deterioration in a laboratory value/vital sign/ECG/ECHO or cardiac MRI is associated with clinical signs and symptoms, the sign or symptom will be reported as an AE and the associated laboratory result/vital sign/ECG/ECHO or cardiac MRI will be considered as additional information. Wherever possible the reporting investigator uses the clinical, rather than the laboratory term (eg, anaemia versus low haemoglobin value). In the absence of clinical signs or symptoms, clinically relevant deteriorations in non-mandated parameters should be reported as AE(s).

Deterioration of a laboratory value, which is unequivocally due to PD, should not be reported as an AE/SAE.

Any new or aggravated clinically relevant abnormal medical finding at a physical examination as compared with the baseline assessment will be reported as an AE unless unequivocally related to the disease under study.

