#### **9.4.3.4 Laboratory Parameters**

Laboratory parameters will be presented for each treatment group. Summary statistics for continuous variables cover n, mean, SD, min, Q1, median, Q3, and max.

For each scheduled post-baseline visit, descriptive statistics for all clinical chemistry and haematology parameters will be presented for observed values and change from baseline.

Details of laboratory analyses will be provided in the SAP.

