#### **9.4.3.5 Other Safety Endpoint(s)**

Other safety data, including ophthalmologic assessments, will be summarised using descriptive statistics.

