4.6.4.2 Presentations

Urinalysis data will only be listed, and no summary tables will be produced. Site reference ranges will also be listed. Flags (H or L) will be applied to values falling outside the reference ranges (which will be explicitly noted on these listings where applicable), and to values for which CTCAE grading applies.

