4.6.9.2 Presentations

Only intraocular pressure will be presented graphically using box plots for absolute values and changes from baseline by treatment group and scheduled visits for each treatment period, split by right eye and left eye within the same plot.

Only on-treatment ophthalmologic examination data as defined in Section 3.3.2.3 are included in the figure. The same section describes the treatment period definitions and further information on the presentation of the tables.

Ophthalmology examination data will be listed for patients, including a description of the abnormalities and relevant baseline result.

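### The protocol promises descriptive summaries of the ophthalmologic assessments, but the SAP shows only intraocular pressure by arm, lists visual acuity and fundoscopy, and does not declare the change

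*Protocol*

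**What the plan says.** **Protocol.** The safety objective in the Synopsis, repeated in Section 3 (Table 4), is comparative: "To assess the safety and tolerability of selumetinib alone and as compared to placebo in adult participants with NF1". Its ophthalmologic measures are set out as "Ophthalmologic assessments include best corrected visual acuity, IOP, and slit-lamp fundoscopy", and the attribute to be covered is the observed value. On laboratory data the same table says "Laboratory parameters include clinical chemistry and haematology parameters as well as urinalysis", to be covered as observed value and change from baseline. Section 9.4.3.5 commits to a summary: "Other safety data, including ophthalmologic assessments, will be summarised using descriptive statistics". Section 9.4.3.4 is narrower on laboratory data. By visit, "descriptive statistics for all clinical chemistry and haematology parameters will be presented for observed values and change from baseline", and urinalysis is not named.

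Section 8.3.5 restricts which deteriorations in mandated tests, eye examinations included, go on the AE form. They "should therefore only be reported as AEs if they fulfil any of the SAE criteria", lead to discontinuation of treatment, or are judged clinically relevant by the investigator.

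**SAP.** Section 4.6.9.2 says "Only intraocular pressure will be presented graphically using box plots", by treatment group and visit. The ophthalmology data otherwise go into a listing that gives the abnormality and the relevant baseline result. Section 4.6.4.2 says "Urinalysis data will only be listed, and no summary tables will be produced". Section 2, on changes from the protocol's planned analyses, mentions neither.

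**The concern.** Retinal toxicity is a named risk in protocol Table 3, and ocular toxicity is an AE of special interest (AESI) in Table 9. The first 12 cycles are the only period with a placebo comparator. Two of the three ophthalmologic measures that the protocol names for its comparative safety objective, visual acuity and fundoscopy, have no by-arm display planned outside the AE tables.

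A patient listing is a poor substitute. Exclusion criterion 11(d) accepts participants whose eye findings come from long-standing optic pathway glioma or orbito-temporal PN. Some will be abnormal at entry, and a reader of the listing has to separate old findings from new ones and then count by arm unaided. A modest excess of small acuity losses or minor fundus changes on selumetinib could sit in the listing unnoticed.

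**Working it through.** The plan states no figure on this point, so nothing needs to be reproduced. The check sets the commitments beside the planned outputs.

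| Measure | Protocol endpoint table | Protocol Section 9 | By-arm display in SAP (outside AE tables) | Listed | Departure declared in SAP Section 2 |
|---|---|---|---|---|---|
| Intraocular pressure | Observed value | Summary (9.4.3.5) | Box plots of values and changes | Yes | Not applicable |
| Visual acuity | Observed value | Summary (9.4.3.5) | None | Yes | No |
| Slit-lamp fundoscopy | Observed value | Summary (9.4.3.5) | None | Yes | No |
| Urinalysis | Observed value and change | Not named (9.4.3.4) | None | Yes | No |

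**Is a summary provided elsewhere in the SAP?** Table 1 assigns ophthalmologic assessment to the Randomised Period SAF and the On-Selumetinib SAF, and Section 4.6 says tables are produced for both sets. Section 4.6.9.2 then specifies one figure and a listing, and no table. The SAP therefore points to tables it does not define. For urinalysis, Table 17 drives the laboratory shift tables and box plots and contains no urine parameter.

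**Is the omission deliberate and recorded?** The only ophthalmology entry in the SAP amendment history concerns plotting intraocular pressure by eye. The protocol's amendment history records that physical-examination summaries were removed from Section 9.4.3.5 as not required. The ophthalmologic sentence in that section still stands.

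**What does the AE route catch?** A deterioration becomes an AE if it is serious, causes discontinuation or is judged clinically relevant (protocol 8.3.5). The ocular AESI terms in Table 9 are broad and include general visual impairment and eye disorder. SAP Section 4.6.2.2 tabulates AESIs by arm, and by maximum CTCAE grade, for both safety periods. The review for other significant AEs (SAP 4.6.2.1) covers laboratory, vital-sign and ECG data by expert judgement, and eye examinations are not named. What remains uncompared is therefore acuity and fundoscopy change below the AE threshold.

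**How much data is involved?** Protocol Table 1 schedules eye examinations at screening, Cycle 6 and Cycle 12, plus end of treatment for those who stop. With the planned 73 participants per arm and two scheduled post-baseline examinations in the randomised period, the upper limit is 73 × 2 = 146 scheduled examinations per arm, if nobody drops out or misses one.

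**The case against.** **The ocular risk already has a by-arm comparison.** This stands, and it sets the limit of the point. A reader might infer that retinal toxicity is never compared between selumetinib and placebo. The documents do not support that, because anything serious, treatment-ending or clinically relevant reaches the AE and AESI tables.

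**The AE rule itself relies on these summaries.** A reader might infer from protocol 8.3.5 that eye findings are kept off the AE form because the study report will summarise them. The sentence on summaries names laboratory tests, vital signs, physical examinations, ECGs and cardiac imaging. Ophthalmologic examinations appear only in the next sentence, on AE reporting. The commitment for eye data comes from Section 9.4.3.5 alone. Urinalysis, as a laboratory test, does fall under the 8.3.5 sentence.

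**The protocol asks for less than shift tables.** This is partly right. For ophthalmology the endpoint table lists the observed value only, so a plain descriptive table would honour the commitment. Baseline-to-worst displays are recommended because they are easier to interpret in this population. A bare normal/abnormal shift would be weak, since it cannot show worsening in someone abnormal at entry.

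**Urinalysis follows Section 9.4.3.4.** This is largely right. That section limits by-visit statistics to chemistry and haematology, Table 3 names no urinary risk, and laboratory data get the expert review for other significant AEs. The conflict is with the endpoint table and the laboratory wording of 8.3.5, so the point is secondary.

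**The outputs may be specified elsewhere.** The interim SAP holds lists of outputs by data cut-off and is not available here. SAP 4.6.9.2 does not expressly exclude tables, as 4.6.4.2 does for urinalysis. This remains possible, but the main SAP should then say so.

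**Conclusion.** The point holds as an undeclared departure of the SAP from protocol Section 9.4.3.5 for visual acuity and slit-lamp fundoscopy. Two of three ophthalmologic measures have no by-arm summary, and the loss is confined to findings below the AE reporting threshold. It matters most in the randomised period, where the placebo comparison exists.

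No number of missed events can be given. The documents state no rate of sub-threshold eye findings, and Table 3 describes the retinal events only as isolated cases, so any assumed split between arms would be invention. The safety analysis is descriptive, so no test or power is at issue, and no efficacy conclusion changes.

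The conclusion assumes that the interim SAP and the table shells do not already contain these tables. Urinalysis is a minor inconsistency to tidy up at the same time.

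**What to change.** In SAP Section 4.6.9.2, add by-arm descriptive tables for the Randomised Period SAF and the On-Selumetinib SAF:

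- **Visual acuity:** observed value by visit and worst on-treatment change from baseline, by eye.
- **Fundoscopy:** baseline to worst on-treatment result, counting new or worsened abnormalities, so that participants abnormal at baseline also contribute information.

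In SAP Section 4.6.4.2, either add a baseline-to-worst shift table for urine protein, blood and glucose, or state in SAP Section 2 that urinalysis will be listed only, and why. If the ophthalmology tables are not wanted, that departure should likewise be declared and justified in Section 2.

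The cost is a few standard tables from data already collected, in the style the SAP uses for ejection fraction and ECOG status. No extra assessments are needed, and there is no effect on sample size or the testing procedure.
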